### 9.1.3 Exploratory endpoints

Endpoint	Time frame	Unit
Number of AEs related to hepatic or renal function during the study period	From inclusion of the patient until end of study	Count of events
Number of physician-identified AEs related to the system organ class "Nervous system" or significant	From inclusion of the patient until end of study	Count of events

Protocol  
 NN7088-4029  
 UTN: U1111-1235-6007  
 EU PAS No.

~~CONFIDENTIAL~~

Date: 17 April 2020  
 Version: 2.0  
 Status: Final  
 Page: 19 of 49

**Novo Nordisk**

deviations from expected neurologic function during the study period

Changes in laboratory parameters during the study period, including hepatic and renal function parameters	From inclusion of the patient until end of study visit	Count of events
---	--	-----------------

PEG-plasma levels	At entry, after 2 years, and at the end of study	ng/mL
-------------------	--	-------

Number of FVIII treatment requiring bleeding episodes reported during the study period	As described in section 9.2.7.1	Count of events
--	---	-----------------

#### 9.1.4 Treatment of patients

Patients will be treated with commercially available N8-GP for prophylaxis and treatment of bleeding episodes according to routine clinical practice at the discretion of the treating physician. Patients may undergo surgical procedures while participating in the study.

As this is a non-interventional study, there is no prohibited concomitant medication during participation. If the treating physician decides to use other FVIII replacement therapy products or combination therapy with N8-GP or additional haemostatic agents, any concurrent medications (including other FVIII products, anti-fibrinolytics, topic haemostatic products or sealants) should be documented by the study site.

Patients who develop FVIII inhibitors can continue treatment with N8-GP at the discretion of the physician. If this is decided, the dosing and dosing frequency will be decided by the treating physician based on the clinical evaluation.

## 9.2 Setting

### 9.2.1 Study Population

Planned number of patients to be included:	60
--	----

Planned number of patients to complete the study:	50
---	----

Anticipated number of patients to be included in each country: Depending on availability in relevant countries

Time period for the study:	Estimated to 7 years
----------------------------	----------------------

Protocol  
 NN7088-4029  
 UTN: U1111-1235-6007  
 EU PAS No.

~~CONFIDENTIAL~~

Date: 17 April 2020  
 Version: 2.0  
 Status: Final  
 Page: 20 of 49

**Novo Nordisk**

### 9.2.2 Inclusion criteria

1. Signed consent obtained before any study-related activities (study-related activities are any procedure related to recording of data according to the protocol).
2. The decision to initiate treatment with commercially available Esperoct® has been made by the patient/Legally Acceptable Representative (LAR) and the treating physician before and independently from the decision to include the patient in this study.
3. Male patients of all ages, according to local label, are allowed in this study
4. Diagnosis of severe or moderate Haemophilia A

### 9.2.3 Exclusion criteria

1. Previous participation in this study. Participation is defined as having given informed consent in this study
2. Known or suspected hypersensitivity to N8-GP or related products
3. Mental incapacity, unwillingness or language barriers precluding adequate understanding and cooperation
4. Clinical suspicion or presence of FVIII inhibitors at time of inclusion

### 9.2.4 Rationale for selection criteria

The study is intended to reflect the population for which N8-GP is approved and marketed in the various countries, therefore study participants can be recruited regardless of their age as long as N8-GP is prescribed by the physician according to local label. In general, all patients from pre-authorisation clinical studies could be enrolled in post-marketing investigations.

Patients who previously developed inhibitors can be included after successful ITI. The proportion of ITI patients should not be more than 25% of the whole cohort.

The few inclusion and exclusion criteria will reduce selection bias. As a multicentre, multinational population has been selected the generalizability of the study is evaluated as high. The study is global and can include all ethnic groups.

#### **The study population is characterized through the inclusion criteria:**

Criterion no. 1 is included in accordance with Good Pharmacoepidemiology Practices (GPP)

Criterion no. 2 is included in accordance with Good Pharmacovigilance Practice (GVP) and based on the EMA guideline concerning post-marketing investigation and expanded for the purpose of reflecting local clinical practice

Criterion no. 3 is included to reflect the population for which N8-GP is approved and marketed in the respective countries.

Protocol  
NN7088-4029  
UTN: U1111-1235-6007  
EU PAS No.

~~CONFIDENTIAL~~

Date: 17 April 2020  
Version: 2.0  
Status: Final  
Page: 21 of 49

**Novo Nordisk**

Criterion no. 4 is included based on the EMA guideline concerning post-marketing investigation and expanded for the purpose of reflecting local clinical practice

**The study population is characterized through the exclusion criteria:**

Criterion no. 1 is to ensure that a patient only counts once in the data analyses

Criterion no. 2 is included in accordance with International Conference on Harmonisation/Good Clinical Practice (ICH-GCP)

Criterion no. 3 serves to protect patient safety by eliminating the risk of not following prescribed dosing of N8-GP.

Criterion no.4 is derived from the EMA guideline concerning post-marketing investigation

**9.2.5 Withdrawal criteria**

The patient may withdraw - or the parent(s)/LAR may withdraw the patient - at will at any time.

In case of withdrawal, the physician should attempt to collect any outstanding data. The primary reason (adverse event or other) for discontinuation should be specified in the Case Report Form (CRF).

Protocol  
 NN7088-4029  
 UTN: U1111-1235-6007  
 EU PAS No.

~~CONFIDENTIAL~~

Date:  
 Version:  
 Status:  
 Page:

17 April 2020  
 2.0  
 Final  
 22 of 49

**Novo Nordisk**

## 9.2.6 Visit procedures

**Table 9-1 Flow Chart**

Visit	Section	Baseline	Visits	Follow-Up
		Visit 1	Visit 2.1, 2.2, 2.3 etc	Visit 3 (End of Study)
PATIENT RELATED INFORMATION AND ASSESSMENTS				
Informed Consent	9.2.8.1	X		
In/exclusion Criteria	9.2.2 9.2.3	X		
Medical history	9.2.8.2	X		
Haemophilia treatment and bleed history	9.2.8.3	X		
Details of Haemophilia	9.2.8.4	X		
Demography	9.2.8.5	X		
Concomitant illness	9.2.8.6	X		
Concomitant medication	9.2.8.7	X	X	X
Withdrawal criteria	9.2.5		X	X
Genotype a	9.2.8.8	X		
Dosing regimen	9.2.8.9	X	X	X
Body measurements	9.2.8.10	X	X	X
EFFECTIVENESS				
Bleeding episode b	9.2.7.1	X	X	X
SAFETY				
FVIII inhibitor	9.2.7.2	X	X	X
Factor VIII Activity	9.2.7.3	X	X	X
PEG plasma level c	9.2.7.4	X	X c	X
Biochemistry	9.2.7.5	X	X	X
Urinalysis	9.2.7.6	X	X	X
Physical examination	9.2.7.7	X	X	X
Adverse event	9.2.7.8		X	X
OTHER ASSESSMENTS				
Surgery	9.2.8.11		X	X
REMINDERS				
Discuss content and use of patients own diary	9.2.7.1 , 9.2.8.9	X	X	
End of study				
	9.2.6.4			X

a) Only the FVIII genotype should be captured if available as existing result in medical records.

Protocol  
 NN7088-4029  
 UTN: U1111-1235-6007  
 EU PAS No.

~~CONFIDENTIAL~~

Date: 17 April 2020  
 Version: 2.0  
 Status: Final  
 Page: 23 of 49

**Novo Nordisk**

- b) Only FVIII requiring bleeding episodes must be captured including bleed details and severity rating where available.
- c) One measurement two years after enrolment and if considered clinically warranted by the responsible physician.

Informed consent is required when entering the study. The rest of the assessments listed in the flow chart are not mandatory, but it is recommended to monitor safety of N8-GP in participating patients. Information from assessments performed during the patient's participation in the study should be recorded in the eCRF from the time informed consent has been obtained. For each visit the site personnel should enter all available information in the eCRF as specified in the below sections.

Patients should receive care at their respective clinic in accordance with local clinical practices. All study visits should be performed according to local clinical practice. The physician should keep a patient enrolment log and a log of patients evaluated for, but not included in the study, throughout the enrolment period. These logs may be separate or combined in one document. Patient identification is to be accomplished via allocation of a six-digit number which consists of a three-digit site code and a three-digit patient ID. A range of numbers will be provided by Novo Nordisk.

Signed informed consent must be obtained from the patient or, for patients under legal age, from the parent(s) or LARs prior to any study related activities.

Patients enrolled in the study should be provided with contact address(es) and telephone number(s) of the physician site and/or staff. In case a patient is being prematurely withdrawn from the study the physician should ensure that the procedures for the last visit are recorded, if possible.

#### **9.2.6.1 Baseline (Visit 1)**

Relevant data available in the patient's medical record at the time of the baseline visit may be used as baseline data and should be entered in the eCRF after having obtained informed consent. All relevant data necessary for evaluating whether a patient can be enrolled in the study e.g. inclusion/exclusion criteria, see section [9.2.2](#) and [9.2.3](#), must be available prior to enrolling a patient. Relevant data regarding the assessments listed in the flow chart for visit 1 must be entered in the eCRF, if available.

#### **9.2.6.2 Visits 2.1, 2.2, 2.3, etc.**

At each contact with the site during the study, the patient should be asked about possible adverse events since the last contact. This may be done by posing a simple question such as "have you experienced any problems since the last contact?".

Relevant data regarding the assessments listed in the flow chart must be entered in the eCRF, if available.

Protocol  
 NN7088-4029  
 UTM: U1111-1235-6007  
 EU PAS No.

~~CONFIDENTIAL~~

Date: 17 April 2020  
 Version: 2.0  
 Status: Final  
 Page: 24 of 49

**Novo Nordisk**

### **9.2.6.3 Phone contacts**

In case a patient calls the site during his participation in the study all relevant study information, i.e. reported AEs, should be entered in the patients' medical records and subsequently in the eCRF.

### **9.2.6.4 End of study visit**

This visit will take place just prior to the planned study LPLV date. In case a patient withdraws his consent, the physician should encourage the patient to come in for an end of study visit. Relevant data regarding the assessments listed in the flow chart must be entered in the eCRF, if available.

The end of study visit may, if not possible to be conducted as an on-site visit, be performed as a phone contact. This should only be done in case a patient does not visit the site as part of his routine care.

#### **The following must be reviewed and recorded:**

- End of study form
- Withdrawal criteria, in case a patient has withdrawn, section [9.2.5](#)

### **9.2.7 Assessments for safety and effectiveness**

#### **9.2.7.1 Bleeding episodes**

The physician should at each visit ask the patient if he has experienced any FVIII treatment requiring bleeding episodes since his last visit. The physician should encourage the patient to note down the date, cause and anatomical location of each FVIII treatment requiring bleeding episodes between the visits in his own personal notes/diary. This information should be entered into the eCRF.

#### **9.2.7.2 FVIII inhibitor**

In case a FVIII inhibitor test is performed as part of the local clinical practice the result should be recorded in the eCRF. A patient has confirmed inhibitor if the patient has been tested positive for inhibitors at two consecutive tests 1-4 weeks apart. Even if the second inhibitor test is positive, the patient may continue treatment with N8-GP.

A positive inhibitor test considered related to N8-GP should be reported as a serious adverse event (SAE) regardless of confirmation, see section [11](#). Any potential follow-up inhibitor testing should be reported as a follow-up to the reported SAE, see section [11](#).

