**Novo Nordisk**

## 8.2 Secondary objective

To further evaluate the general safety including FVIII inhibitors and allergic/hypersensitivity reactions of N8-GP during routine use in patients with haemophilia A under the circumstances for which it was prescribed.

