**Figure 9-1 Study Design**

### 9.1.1 Primary endpoint

Endpoint	Time frame	Unit
Number of Adverse Events (AEs) reported during the study period	From inclusion of the patient until end of study	Count of events

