### 9.1.2 Secondary endpoint

Endpoint	Time frame	Unit
Number of Serious Adverse Events (SAEs) reported during the study period	From inclusion of the patient until end of study	Count of events

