**Novo Nordisk**

### **Serious Adverse Event (SAE)**

An SAE is an experience that at any dose results in any of the following:

- Death
- Life-threatening experience (actual risk not hypothetically)
- Inpatient hospitalisation or prolongation of existing hospitalisation
- A persistent or significant disability/incapacity or is a congenital anomaly/birth defect
- Important medical events that may not result in death, be life-threatening or require hospitalisation may be considered an SAE, when based upon appropriate medical judgement - they may jeopardise the patient or subject or require medical or surgical intervention to prevent one of the outcomes listed in this definition. Suspicion of transmission of infectious agents must always be considered an SAE.

The following AEs must always be reported as SAEs using the important medical event criterion, if no other seriousness criteria are applicable:

- suspicion of transmission of infectious agents via the trial product.
- risk of liver injury defined as ALT or AST  $>3$  x UNL and total bilirubin  $>2$  x UNL, where no alternative aetiology exists (Hy's law).
- development of FVIII inhibitor either based on local laboratory tests or clinical suspicion, regardless of confirmation

Protocol  
NN7088-4029  
UTN: U1111-1235-6007  
EU PAS No.

~~CONFIDENTIAL~~

Date:  
Version:  
Status:  
Page:

17 April 2020 | **Novo Nordisk**  
2.0  
Final  
49 of 49

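### Section 9.2.7.2 and Appendix A set different conditions for reporting a FVIII inhibitor as an SAE, so the secondary endpoint count and the reporting clock can differ by site

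*Protocol*

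**What the plan says.** The section on inhibitor testing (9.2.7.2) has results from local practice entered in the eCRF and then gives a reporting rule: "A positive inhibitor test considered related to N8-GP should be reported as a serious adverse event (SAE) regardless of confirmation". It refers the reader to section 11.

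Appendix A, under the SAE definition, has its own rule. It opens a short list with "The following AEs must always be reported as SAEs using the important medical event criterion, if no other seriousness criteria are applicable", and one item on that list is "development of FVIII inhibitor either based on local laboratory tests or clinical suspicion, regardless of confirmation".

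The secondary objective (8.2) is "To further evaluate the general safety including FVIII inhibitors and allergic/hypersensitivity reactions of N8-GP during routine use in patients with haemophilia A". The only secondary endpoint (9.1.2) is "Number of Serious Adverse Events (SAEs) reported during the study period". The primary endpoint (9.1.1) is "Number of Adverse Events (AEs) reported during the study period".

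Neither list of adverse events of special interest (AESIs), in section 11.1 or in Appendix A, includes FVIII inhibitors.

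**The concern.** Seriousness and causality are separate judgements, and Appendix A treats them so: an AE need not be related to the product, and causality has its own three-level scale. Section 9.2.7.2 makes a relatedness judgement part of the trigger for an SAE report. It also speaks only of a positive test, whereas Appendix A accepts clinical suspicion as well.

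A site working from the section that deals with inhibitors could apply the narrower rule, and a site working from Appendix A the broader one. Because inhibitors are not AESIs, no second route restores the faster handling when an event is not classed as an SAE. At stake are the comparability across sites of the sole secondary endpoint and the speed at which the sponsor hears of an event that the protocol's background (4.2) names as a specific risk of FVIII replacement.

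**Working it through.** The protocol states no inhibitor rate or target, so there is no figure to reproduce. The check is a comparison of the two texts, followed by a note on scale.

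**1. Which cases are classified differently.** I read *related* as a causality of possible or probable, as Appendix A does when it defines an adverse reaction. All rows assume that no other seriousness criterion is met; if one is, the event is an SAE under either section.

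| Case | Section 9.2.7.2 | Appendix A | Same? |
|---|---|---|---|
| Positive test, possible or probable | SAE | SAE | Yes |
| Positive test, unlikely | Condition not met | SAE | No |
| Clinical suspicion, no positive test | Not addressed | SAE | No |

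The two texts agree that a confirmatory test is not needed. They differ on relatedness, on suspicion without a test, and in force: 9.2.7.2 recommends, Appendix A obliges.

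**2. What changes when such a case is handled as a non-serious AE.**

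- Initial report (11.2): 14 calendar days instead of 24 hours.
- Safety information form (11.1): required for SAEs and AESIs, so not required here.
- New information (11.3): 14 calendar days instead of 24 hours.
- Follow-up (11.3): SAEs, AESIs and non-serious adverse reactions are followed to a final outcome. Other non-serious AEs may stop at recovering or at end of study. This loosening applies to an event judged unrelated; a suspicion judged related would remain a non-serious adverse reaction under the stricter rule.
- Repeat inhibitor tests (9.2.7.2): these are to be reported as follow-up to the SAE, a route that does not exist if no SAE was filed.
- Endpoints: the secondary SAE count falls by 1 per case. The primary AE count changes by 0, provided the event is recorded as an AE.

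**3. Where the affected cases could arise.** Section 9.2.4 admits patients after successful immune tolerance induction, up to 25% of the cohort. With 60 planned (9.2.1), 0.25 × 60 = 15 patients. Section 9.1.4 allows other FVIII products during the study. Both offer an alternative explanation for a positive test, so a judgement of unlikely is plausible. The 15 is a ceiling on such patients, not a forecast of events.

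**4. Scale of one case.** Counts of 0 and 1 are assumptions chosen to show scale. Intervals are exact Clopper-Pearson 95%.

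| Denominator | 0 patients with an inhibitor SAE | 1 patient |
|---|---|---|
| 60 | 0% (0 to 6.0%) | 1/60 = 1.7% (0.04 to 8.9%) |
| 50 | 0% (0 to 7.1%) | 1/50 = 2.0% (0.05 to 10.7%) |

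In a cohort of this size, one reclassified event separates none observed from one observed.

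**The case against.** The strongest reply is that the passages can be read together. Section 9.2.7.2 does not say that unrelated positive tests are not SAEs. It points to section 11, which sends the reader to Appendix A for safety definitions, and section 9.2.7.8 points there too. Appendix A uses the stronger language, so a site that follows it satisfies both. The affected set may also be small: the possible category is broad, and a positive test in a patient on the product escapes it only if judged unlikely. All of this stands, and it makes the matter one of differing conditions rather than outright negation. It does not settle which text governs, and a site that stops at 9.2.7.2 has no signal that a broader rule exists.

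A reader might also infer more than the protocol supports:

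- *That the SAE count is the only endpoint capturing inhibitors.* It is the only endpoint paired with the secondary objective. However, the primary endpoint counts all AEs, the AE definition includes abnormal laboratory findings whether or not related, and all AEs are listed (9.7.2.1).
- *That non-serious allergic reactions escape.* Allergic and anaphylactic reactions of any seriousness are AESIs, and section 9.7.4 has endpoint events summarised separately by class.
- *That the safety analysis set is a wrong denominator for inhibitor incidence.* The protocol fixes no such incidence; the primary and secondary endpoints are counts. Section 9.9 acknowledges that testing follows routine practice, and a denominator of tested patients is a matter a SAP can carry.
- *That inhibitor incidence will be biased down by a known amount.* No figure in the protocol supports a size.

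**Conclusion.** The inconsistency is real and should be corrected. For two kinds of event, a positive test judged unlikely to be related and a clinical suspicion without a positive test, the protocol gives two different answers on SAE reporting. The effect is one unit of the sole secondary endpoint per case, together with the slower and lighter handling set out above. It does not remove the event from the primary endpoint or the test result from the eCRF.

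The conclusion rests on three assumptions: that some sites would apply 9.2.7.2 as it stands, that the event meets no other seriousness criterion, and that an event not reported as an SAE is still recorded as an AE. How many events would be affected cannot be derived from the protocol. It may be none, but the correction does not depend on the number.

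**What to change.** Reconcile section 9.2.7.2 with the SAE list in Appendix A so that one reporting rule applies at all sites. One way is for 9.2.7.2 to drop its own condition and refer to the Appendix A criterion, with causality recorded separately as for any other AE. The sentence on repeat testing can stay, since it would then always have an SAE report to attach to.

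The cost is one sentence in a protocol amendment and a note to sites. No new data, endpoint or analysis is needed. The downside is a possibly slightly higher SAE count.

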#### **9.2.7.3 FVIII activity**

In case FVIII activity is determined as part of the local clinical practice, the result(s) should be recorded in the eCRF.

Protocol  
NN7088-4029  
UTN: U1111-1235-6007  
EU PAS No.

~~CONFIDENTIAL~~

Date: 17 April 2020  
Version: 2.0  
Status: Final  
Page: 25 of 49

**Novo Nordisk**

#### **9.2.7.4 PEG plasma level**

PEG plasma levels should be determined three times during the course of the study. This should preferably be done at baseline (visit 1), after two years of participation in the study and at the 'End of study visit'. Additionally, the responsible physician can request additional analyses if considered clinically warranted. The sample will be analysed at a special laboratory, contracted by sponsor, to determine the concentration of PEG in the patients' blood.

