### 4.3 Research question and objectives

The research question behind the study is to gain additional knowledge on safety in prophylaxis patients and obtain additional clinical data on the use of N8-GP in the setting of local clinical practice.

The primary objective of the study is to investigate the safety of N8-GP including the PEG moiety during prophylaxis and long-term use in patients with haemophilia A as prescribed by the physician.

Secondary objectives are to further evaluate the general safety of N8-GP during routine prophylaxis (including FVIII inhibitors and allergic/hypersensitivity reactions) and long-term use in patients with haemophilia A as prescribed by the physician.

Exploratory objectives are to monitor possible clinical effects of long-term exposure to N8-GP prophylaxis in patients with haemophilia A, including assessments of kidney and liver function parameters, neurological function and patients' PEG plasma level.

The primary endpoint of the study is:

- Number of Adverse Events (AEs) reported during the study period

The secondary endpoint is:

- Number of Serious Adverse Events (SAEs) reported during the study period

The exploratory endpoints are:

- Number of AEs related to hepatic or renal function during the study period
- Number of AEs that are defined within the system organ classes "Nervous system" or significant deviations from expected neurologic function during the study period
- Changes in laboratory parameters during the study period; including the hepatic and renal function parameters
- Changes in PEG-plasma levels from study start to end of study
- Number of FVIII treatment requiring bleeding episodes reported during the study period

Protocol  
NN7088-4029  
UTN: U1111-1235-6007  
EU PAS No.

~~CONFIDENTIAL~~

Date: 17 April 2020  
Version: 2.0  
Status: Final  
Page: 13 of 49

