## 7 Rationale and background

Novo Nordisk has developed turoctocog alfa pegol (also referred to as N8-GP), a 40-kDa glycoPEGylated human recombinant coagulation Factor VIII (rFVIII) with an extended half-life, for the prophylaxis and treatment of bleeding episodes in patients with haemophilia A. N8-GP has improved pharmacokinetic (PK) properties including a 1.6 fold increase in terminal half-life compared with standard FVIII products, which offers the possibility of achieving FVIII levels in the range of moderate haemophilia A with a less burdensome every fourth day or twice weekly treatment regimen.

Marketing authorisation applications for Esperoct® have been submitted globally. Esperoct® was approved in the US in February 2019 followed by EU in June 2019, and Canada and Switzerland in July.

The regulatory approval of N8-GP was based on the comprehensive pathfinder™ programme, a phase 1 to 3a clinical programme including 270 unique previously-treated patients (PTPs) children,

Protocol  
NN7088-4029  
UTN: U1111-1235-6007  
EU PAS No.

~~CONFIDENTIAL~~

Date: 17 April 2020  
Version: 2.0  
Status: Final  
Page: 16 of 49

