#### **9.2.8.9 Dosing regimen**

The N8-GP dosing regimen at study entry and any changes in regimen during the study, must be recorded in the eCRF, including dosing regimen and date.

The physician should at each visit discuss the haemophilia treatment with the patient. The patient should be asked if the prophylaxis doses of N8-GP were taken as prescribed since last visit, and any deviations from the prescription must be recorded in the eCRF.

The physician should ensure that the patient notes down any treatment relevant details between the visits in his own personal notes/diary. The patient diary (for example national mobile application or personal paper diaries) must be used as a basis in the discussion during the routine visits to the clinic.

Protocol  
NN7088-4029  
UTN: U1111-1235-6007  
EU PAS No.

~~CONFIDENTIAL~~

Date: 17 April 2020  
Version: 2.0  
Status: Final  
Page: 28 of 49

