**Novo Nordisk**

Number of these specific AEs during study period will be summarised together with the number of patients with any of these AEs. Furthermore, listings will be provided displaying all these specific AEs.

- Changes in laboratory parameters during the study period, including hepatic and renal function parameters.

Laboratory parameters will be summarised by visit. Furthermore, change from baseline (visit 1) will be summarised. Listings and individual over time profile plots (where deemed relevant) will be provided displaying laboratory parameters reported during the study period.

- PEG-plasma levels at study entry, after two years and at the end of study

PEG plasma level will be summarised by visit. Listings and individual over time profile plots will be provided displaying PEG plasma level reported during the study period.

- Number of FVIII treatment requiring bleeding episodes reported during the study period

Number of FVIII treatment requiring bleeding episodes reported during the study period will be summarised. Furthermore, listings will be provided displaying all FVIII requiring bleeding episodes.

Definition of a bleeding episode: Multiple bleeding locations occurring during the same event (e.g., due to a bicycle accident) or at the same time point will be counted as one bleeding episode. A bleeding which occurs within 72 hours after stopping treatment of a previous bleeding event at the same or a subset of the same anatomical location(s) is considered a re-bleed, and is not a new bleeding episode. If a bleeding event occurs in the same location later than 72 hours after stopping treatment of a previous bleeding event it is considered a new bleeding episode.

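### PEG plasma samples are tied to visits only, not to N8-GP infusions or to the first N8-GP dose, so by-visit changes mix accumulation with exposure status at entry and dose timing

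*Protocol*

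**What the plan says.** **Sampling.** Section 9.2.7.4 asks for three PEG determinations per patient: "This should preferably be done at baseline (visit 1), after two years of participation in the study", with the third at the end-of-study visit. The physician may request more. Footnote c to the flow chart (Table 9-1) sets the middle sample as "One measurement two years after enrolment and if considered clinically warranted by the responsible physician". The endpoint table in section 9.1.3 gives the time frame as "At entry, after 2 years, and at the end of study". All of these are visit or calendar anchors, and visits follow local practice.

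**Exposure at entry.** Section 4.4 admits patients who have already had N8-GP as well as those who have not. The treatment history in section 9.2.8.3 asks for the brand of FVIII product only where an inhibitor emerges.

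**Dosing records.** Section 9.2.8.9 states: "The N8-GP dosing regimen at study entry and any changes in regimen during the study, must be recorded in the eCRF", with dates, together with deviations from the prescription. Section 9.3 derives consumption from the regimen and the reported bleeds. Patients keep their own diary of treatment details, and section 9.4 has available diary information on treatment entered in the eCRF. The last dose before a PEG sample is named nowhere, nor is the date of the first-ever N8-GP dose.

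**Analysis.** The abstract (section 4.3) words the endpoint as "Changes in PEG-plasma levels from study start to end of study". Section 9.7.2.3 says "PEG plasma level will be summarised by visit", with listings and individual profiles over time.

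**The concern.** PEG reaches plasma with each infusion, so a single level has meaning only relative to two facts: how long ago the last dose was given, and how long the patient has been on the product. The protocol fixes neither for the PEG sample.

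Two consequences follow. First, the entry column of the by-visit table can contain patients with no N8-GP exposure, patients a few doses in, and patients at steady state. The change from entry then depends on that mix. Second, a difference between two visits in one patient may partly reflect an early draw on one occasion and a late draw on the other.

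Section 7 gives a theoretical regulatory concern about PEG accumulation as a reason for the study, and section 9.1 says EMA requested the plasma measurement. With three scheduled values per patient there is little to average over. This concerns data that are not requested, so a later analysis plan could not reliably repair it.

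**Working it through.** The protocol states no figure on this point to reproduce. The calculation below only shows how large each effect could be.

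**Inputs**
- Dosing interval τ: 3.5 to 4 days (84 to 96 h), from the background in section 7 ("with a less burdensome every fourth day or twice weekly treatment regimen"). Actual dosing is at the physician's discretion (section 9.1.4), so this is illustrative.
- Plasma PEG half-life h: not in the protocol. Assumed 5 to 15 days, with 2 and 30 days as a wider check.
- Model: one compartment, first-order elimination, equal doses (assumption).

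**1. Swing within one interval at steady state.** Peak/trough = 2^(τ/h). For τ = 4 days:
- h = 5: 2^0.8 = 1.74
- h = 15: 2^0.267 = 1.20

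**2. Spread between two visits with no true change.** If the two draws fall independently and uniformly within the interval, 95% of the differences in position lie within 1 − √0.05 = 0.776 of the interval. The ratio then lies within 2^(±0.776·τ/h). For τ = 4 days:
- h = 5: 2^(±0.621), or 0.65 to 1.54
- h = 15: 2^(±0.207), or 0.87 to 1.15

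**3. Exposure status at entry.** Steady-state peak / first-dose peak = 1/(1 − 2^(−τ/h)).

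| h (days) | τ = 3.5 days | τ = 4 days |
|---|---|---|
| 5 | 1/(1 − 0.616) = 2.60 | 1/(1 − 0.574) = 2.35 |
| 15 | 1/(1 − 0.851) = 6.70 | 1/(1 − 0.831) = 5.93 |

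**4. Effect of mixing on a by-visit summary.** Suppose half the patients are sampled just after a first dose at entry and half are already at steady state, with all later samples at the steady-state peak. The geometric mean ratio is the step 3 ratio to the power 0.5. At τ = 4 days this is √2.35 = 1.5 for h = 5 and √5.93 = 2.4 for h = 15. Neither describes either group: one group has a ratio of 1, the other 2.35 or 5.93.

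**5. Wider check, τ = 4 days.** At h = 2 days, peak/trough is 2² = 4.0 and the step 3 ratio is 1.33. At h = 30 days they are 1.10 and 11.33. The two effects move in opposite directions, so at least one of them matters across the range.

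**The case against.** **Dose timing may be partly recoverable.** A reader might infer that dose times are never captured and that PEG change can therefore never be separated from dose timing. The documents do not support that. Regimen, dated changes and deviations are mandatory, the diary must be the basis of the discussion at visits, and available treatment details go to the eCRF. Concomitant medication (section 9.2.8.7) may also show a switch from another product. What stands is that diary content is unspecified and entry depends on availability, so recovery is possible for some patients but not assured.

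**Other documents may hold it.** eCRF instructions and stand-alone documents exist but are not shown, and a sample form could ask for dose time. That limits certainty; it does not put the requirement in the protocol.

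**The swing could be made to look far larger.** Applying the 1.6-fold FVIII half-life gain in section 7 to an assumed 12 h gives 19.2 h and a 32-fold swing over 96 h. But that is a FVIII half-life, not one for PEG, and it implies an accumulation factor of only 1/(1 − 2^−5) = 1.03, which sits badly with a study of accumulation. It should not be used.

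**Visit 1 may precede exposure in new starters.** Section 9.1 starts safety monitoring at the first N8-GP exposure after consent, and the flow chart has no adverse event entry at visit 1. This hints at the order, but no sentence applies it to the PEG sample, and previously exposed patients remain in the entry column.

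**Post-infusion sampling at visit 1.** A reader might suppose that FVIII activity testing would pull the draw to after an infusion. Section 9.2.7.3 says nothing about when that sample is taken.

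**Site habits.** A habit that is stable over time would largely cancel within a patient, so the step 2 spread is for independent timing only. The protocol supports neither pattern.

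**Status of the endpoint.** PEG is exploratory and descriptive, with no test or decision rule, and section 9.9 already concedes that data follow routine practice. This lowers the weight of the point but does not remove it.

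**Conclusion.** The point holds as a gap in data collection. The protocol ties PEG samples to visits only, leaves the entry sample unplaced relative to the first N8-GP dose, and does not require the last dose before each sample to be recorded.

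Its size depends on a plasma PEG half-life that the protocol does not give. With the assumed 5 to 15 days, dose timing alone is a moderate to small nuisance, and at the long end it would not hide a large change. The undefined exposure status at entry is then the larger problem, with a 2.35 to 6.70-fold difference between a first-dose and a steady-state peak. These figures rest on a simple one-compartment model and the dosing intervals named in the background. Because PEG is exploratory, this is a modest improvement and not a flaw in the primary analysis. It is worth making because the measurement was requested by EMA and the missing facts cannot be relied on to turn up later.

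**What to change.** In section 9.2.7.4 and the eCRF:
- Record the date and time of each PEG sample.
- Record the date, time and IU of the last N8-GP infusion before it.
- Record the date of the patient's first-ever N8-GP dose.
- Ask that samples preferably be drawn before that day's infusion and, in patients not yet on N8-GP, before the first dose. This concerns the blood draw only and changes no treatment.

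In section 9.7.2.3:
- Keep all samples in the analysis.
- Show PEG level against time since last dose.
- Summarise entry values separately for patients unexposed and already exposed to N8-GP.

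The cost is a few eCRF fields and a few sentences, with no extra visit or sample. Some samples will still not be pre-dose, but with the dose time recorded they remain interpretable.
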